2.3 Grouping Criteria

Inclusion Criteria:

- Age > 18 years old, ≤ 75 years old
- Having received MHD treatment in this dialysis center for more than 3 months and maintaining stable condition
- Having normal comprehension ability, clear verbal expression, informed consent and willingness to participate in this study
- Having free movement ability, and being able to tolerate Baduanjin exercise after cardiopulmonary exercise test
- Right-handed, with fistula in the non-dominant hand

Exclusion Criteria:

- Patients who usually practice traditional Chinese medicine exercises such as tai chi;
- Patients who are recently complicated with severe infections, active malignant tumors, severe cardiopulmonary insufficiency, gastrointestinal bleeding, nervous system diseases and cannot tolerate exercise;
- Patients with various orthopedic, neurological, and other diseases that cause muscle and joint deformities that affect grip strength measurement;
- Patients with senile dementia, hearing impairment, comprehension abnormalities, mental disorders, unclear verbal expression or unwilling to participate in this study;
- Patients with hemoglobin < 70g/L, carbon dioxide binding capacity < 13mmol/L, and blood potassium > 6.5mmol/L in laboratory tests and no significant improvement after treatment;
- Patients who are participating in other clinical studies.

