2.6 Preservation and Confidentiality of Information

The researcher preserves all research data, including confirmation of all participants (able to effectively verify different record materials, such as hospital original records), all original informed consent forms with subject signatures, all case

[键入文字]

observation forms, detailed records of evaluation indicators, etc.

The results of this project may be published in medical journals, but we will keep the information of the subjects confidential in accordance with legal requirements. Unless required by relevant laws, the personal information of the subjects will not be disclosed. When necessary, research supervision and management departments, hospital ethics committees and their relevant personnel may access patient information in accordance with regulations.

3. Exit and Termination Criteria

1. patients with adverse reactions such as trauma, surgery or serious infection, cardiopulmonary failure, who cannot continue to perform exercise during the trial;
2. Patients who underwent kidney transplantation or disappeared or died for various reasons during the trial;
3. Patients with poor compliance during the trial, unwilling to continue to exercise or requesting to withdraw from the trial for various reasons.

4 Ethical issues

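### Does the 'and' in the laboratory exclusion leave eligibility open for patients with only one or two unresolved abnormalities?

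*Combined protocol and SAP*

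**What the plan says.** The laboratory exclusion in section 2.3 names three limits in a comma series closed by 'and': "Patients with hemoglobin < 70g/L, carbon dioxide binding capacity < 13mmol/L, and blood potassium > 6.5mmol/L in laboratory tests". The treatment clause then follows directly: "blood potassium > 6.5mmol/L in laboratory tests and no significant improvement after treatment". The bullet does not state whether one value is enough or all three are needed.

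Other bullets in the same exclusion list bear on how its connectives are used:

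- The orthopaedic bullet refers to "various orthopedic, neurological, and other diseases that cause muscle and joint deformities".
- The dementia bullet ends with "mental disorders, unclear verbal expression or unwilling to participate in this study".
- The infection and tumour bullet ends with "gastrointestinal bleeding, nervous system diseases and cannot tolerate exercise".

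Two inclusion criteria in section 2.3 also apply to every candidate. Dialysis at the centre must have lasted "for more than 3 months and maintaining stable condition", and the patient must qualify as "being able to tolerate Baduanjin exercise after cardiopulmonary exercise test".

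**The concern.** Under strict logic, A and B and C and D is true only when all four parts are true. On that reading, a patient with severe anaemia alone, or with high potassium alone, that has not responded to treatment is not caught by this bullet. No other part of the supplied text sets a laboratory limit, and the exit criteria in section 3 contain none. The scope of the treatment clause is a second open point: it could qualify potassium only or the whole list.

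Two matters would be at stake. Screeners who read the bullet differently would decide differently on the same results, so enrolment could not be reproduced or audited against the text. Some patients with a serious unresolved abnormality might also be allocated to an exercise programme that this bullet was meant to keep them out of.

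**Working it through.** The plan states no figure on this point, so there is none to reproduce. The check has three parts.

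**1. How far apart the readings are.** The only input is the bullet itself: three values and one treatment clause. Looking only at abnormalities that have not improved, the number of non-empty patterns is 2^3 − 1 = 7. Requiring all three together excludes 1 of the 7. Accepting any one excludes all 7.

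To bring in the treatment clause, give each value three states: normal, abnormal but improved, and abnormal and not improved. That makes 3^3 = 27 profiles.

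| Reading | Calculation | Profiles excluded |
|---|---|---|
| All three together, clause on all | 1 × 1 × 1 | 1 |
| All three together, clause on potassium only | 2 × 2 × 1 | 4 |
| Any one, clause on all | 27 − 2^3 | 19 |
| Any one, clause on potassium only | 27 − 1 × 1 × 2 | 25 |

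These counts give every profile equal weight. They show that 'and' and 'or' differ, which was never in doubt. They do not say how many of the 50 planned patients would be affected, and nothing in the documents allows that to be estimated.

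**2. Which reading the text supports.**

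- *One value or all three.* The exclusions are written as plural classes of patients followed by a list, a form that normally applies to each item in turn. In the orthopaedic bullet, 'and' joins disease types that nobody would require together. The same holds for the illnesses in the infection and tumour bullet. The one contrast is 'or' in the dementia bullet. There it joins a list of conditions to something of a different kind, unwillingness to take part, so it is weak evidence that 'and' is meant strictly elsewhere. A three-way conjunction would also leave each limit without effect unless the other two were breached.
- *Scope of the treatment clause.* The reference to laboratory tests stands between potassium and the clause. All three values are laboratory values, so that phrase closes the whole list, and what follows most naturally applies to the list. If 'any one' is accepted, the choice of scope moves 25 − 19 = 6 profiles. In all six, every abnormal value has improved. The scope question therefore does not decide whether a patient with an unresolved abnormality is excluded.

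**3. What depends on the answer.** Section 2.2 has patients included and then randomised, 25 to each group. If eligibility is decided without knowledge of the allocation, a lenient or a strict reading shifts the study population in both arms alike and creates no difference between them. The comparisons in section 2.5 are the same under every reading.

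**The case for a change.** The strongest case is that a probable intention is not a written rule. 'Any one' has to be inferred, the treatment clause must still be interpreted, and significant improvement is not defined. The two inclusion criteria rest on judgement and carry no laboratory value. Nor can one team's consistent habit be assumed: section 2.3 speaks of a single dialysis centre, while section 4.1 refers to several centres and sub-centres. The bullet governs entry to a trial in which half the patients exercise three days a week, with measurements up to month 12.

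Much of this is right as description. The bullet could be clearer, and no other passage settles it. What does not follow is a consequence large enough to require a change. A screener would have to choose the least natural reading and also judge the patient stable and able to tolerate the exercise. Sessions are doctor-supervised under section 2.2, and half of those randomised stay on routine treatment. Nothing in the documents suggests that such a patient would be enrolled. If centres did read the bullet differently, they would differ in whom they enrol, before allocation.

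The infection and tumour bullet raises a separate and lesser point. Its closing words on exercise may be their own criterion or a condition on the listed illnesses. The exit rule in section 3 words the matter as a condition: "serious infection, cardiopulmonary failure, who cannot continue to perform exercise during the trial". A patient who cannot tolerate the exercise fails the inclusion criterion on either reading. The readings differ only for a patient with a listed illness who can exercise, and the stability requirement still applies to that patient.

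**Conclusion.** The wording is ambiguous, but no change to the plan follows. The natural reading is that any one of the three unresolved abnormalities excludes, with the treatment clause covering the whole list. Screeners can be expected to apply it that way. The number of patients affected cannot be derived from the documents, and the effect on the stated design figures and on the planned comparison is nil.

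This rests on two assumptions: that screening decisions are made before allocation is known, and that the stability and exercise-tolerance criteria are applied as written. Spelling out the logic on the screening form would be ordinary housekeeping. It would record what is already the sensible reading, leave every limit as it stands, and alter no conclusion of the trial.

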2.4 Outcome Measures

Primary Outcome Measure:

1) Muscle strength measurement

Grip strength can reflect the strength of hand muscles. The grip strength of both hands of patients was measured using a domestic gripper. The patient took an upright position and grasped the handle with the maximum force. When the display on the machine stopped changing, the value was recorded. The test was repeated three times, and the maximum value was taken to record the results.

2) Five-times Sit-to-Stand Test (FTSST)

The five-times sit-to-stand test is used to evaluate the functional strength of the lower

limbs. MHD patients sat on a 46cm chair without armrests, with their feet on the ground and their backs not resting on the chair. Their hands were crossed on their shoulders. They stood up from the chair as quickly as possible without arm support. They completed five sitting and standing movements, and the completion time was recorded. During the test, the patient kept his hands crossed and his knees completely straightened. Three tests were completed, with a one-minute rest between tests. The average value of the three tests was statistically analyzed.

3) Timed "up and go" test (TUGT)

The timed "up and go" test is often used to evaluate functional mobility such as balance and walking required in daily life. MHD patients were seated in a back chair with armrests (the seat was about 46cm high, and the armrest was about 21cm high). A guide line was placed on the ground 3m away from the chair. After the test began, the patient left the chair, stood firmly and walked forward for 3m as fast as possible, crossed the guide line, turned around, and returned to the chair to sit down. The walking aids were not allowed during the test. The test was conducted 3 times in total, with a 1-minute rest between adjacent tests. The average value of the 3 tests was taken for statistical analysis.

4) The sitting forward flexion test

The sitting forward flexion test is often used to evaluate the flexibility of the lower limbs of patients. The patient straightened the knee joint, sat on the flat ground with both feet flat on the test board, bent forward, straightened both arms forward, and gradually pushed the cursor with both middle fingertips to the farthest possible distance. The measuring device was 0 point along the plane of the foot pedal board, negative inward, positive forward, in centimeters. The knee joint could not be bent during the test, and sudden force could not be applied. The test was conducted 3 times in total, and the best result was taken for statistical analysis.

5) The Standing on one-leg with eyes closed test (SOLECT)

The Standing on one-leg with eyes closed test evaluates the stability of the static posture by quantitative measurement, reflecting the balance ability of patients. The patient spread both hands, closed his eyes, and stood on one leg, with the other leg bent so that the angles between the two legs were 90 degrees. Time was recorded from the time when the foot left the ground, and the shaking stopped when the foot left the ground or stood up. The average of the three times was used for statistical analysis.

6) Bone mineral density test

The signals received by the scanning system after the double-energy DXA line penetrated the body were transmitted to the supporting software to calculate the average bone mineral density content (g/cm²) of the whole body, the left femur Ward triangle area, and the lumbar spine (L2~L4).

Secondary Outcome Measures:

1) Changes in the Short Form-36 (SF-36)

Changes from the Short Form-36 (SF-36) and European Quality of Life Five Dimension (EQ-5D-5L) scale at 0 months, 6 months, 12 months. The SF-36 score is used to evaluate an individual's health status and quality of life. The SF-36 score expressed as a number between 0 and 100, with higher numbers indicating better health. EQ-5D-5L evaluate quality of life from five aspects: action ability, self-care, daily activities, pain or discomfort, anxiety or depression. The score range generally ranges from less than 0 to 1, and the higher the score, the better the state; The VAS score range is 0-100, with higher scores indicating better health status.

2) Changes in the Hospital Anxiety and Depression Scale (HADS)

Changes from HADS Index at at 0 months, 6 months, 12 months. HADS consists of 14 items, of which 7 items assess depression and 7 items assess anxiety. The scores for anxiety and depression range from 0 to 21, with higher scores indicating more severe symptoms.

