The Effect of Baduanjin on Physical Fitness and Bone Density in Maintenance Hemodialysis Patients

Affiliated Hospital of Nantong University

2023-07-10

The Effect of Baduanjin on Physical Fitness and Bone Density in Maintenance Hemodialysis Patients

1. Research Background

Chronic kidney disease bone mineral metabolism disorders exist in maintenance dialysis (MHD) patients, with a high incidence of bone and joint pain of 58.7%. At the same time, the motor ability of patients with chronic kidney disease decreases as the disease progresses, and MHD patients gradually experience muscle atrophy, decreased upper limb motor ability, slow walking, and slow sitting and standing. Long term lack of exercise further exacerbates bone and joint lesions. Functional fitness refers to the comprehensive physiological functions of the body's cardiopulmonary, skeletal muscle system and the quality of softness and balance, and is now mainly targeted at the elderly and the frail; it evaluates the level of daily life activities, reflects the decline of body functions, and is an important indicator of health.

Studies have shown that exercise can improve joint function, alleviate joint pain, increase muscle strength, and improve inflammation in MHD patients. However, due to the lack of relevant evidence-based evidence, exercise rehabilitation has not yet been included in routine clinical care plans. Clinical research data on rehabilitation exercises for MHD patients are needed to recommend reasonable, feasible and acceptable exercise modalities for the national population. Baduanjin is an ancient health art that combines breathing and exhaling with physical exercise, and it is a multifactorial intervention that integrates physical, mental, emotional, spiritual and behavioral elements, with moderate exercise volume, which belongs to the category of aerobic exercise. Although studies have suggested that Baduanjin has a good therapeutic effect on people with physical fitness disorders, and clinical studies on the prevention of bone loss and the improvement of bone mineral density have also been conducted gradually. However, there is still a lack of information on the application of Baduanjin in MHD patients. However, there is still a lack of information on the application of Baduanjin in MHD patients.

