2.2 Study Description

The aim of this study is to observe the therapeutic effect of Baduanjin on improving physical fitness and bone density in MHD patients. A total of 50 MHD patients will be included and randomized into an intervention group of 25 cases and a control group of 25 cases. The intervention group undergo a 30 minute Baduanjin exercise under the guidance of a professional doctor before the dialysis day, including a 5-minute warm-up exercise, a 20 minute Baduanjin exercise, and a 5-minute relaxation exercise. The intervention group practice three days a week, while the control group maintain routine treatment and daily activities. Measure the indicators of each group at baseline, months 6, 12. The evaluation of physical fitness is based on the scores (which include muscle strength measurement; five-times sit-to-stand test; timed "up and go" test; sitting forward flexion test; standing on one-leg with eyes closed test). The bone mineral density test is based on the result of the double-energy DXA line. The quality of life score is based on the SF-36 score, and the emotional

score is based on the anxiety and depression scale.

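### FTSST and TUGT have no analysis value for a patient who attends but cannot perform the test, which may bias both comparisons if inability differs between arms

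*Combined protocol and SAP*

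**What the plan says.** Section 2.4 lists FTSST and TUGT among the primary outcome measures.

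- **FTSST.** The patient keeps the hands crossed and completes five stands: "They stood up from the chair as quickly as possible without arm support". The result is a completion time: "The average value of the three tests was statistically analyzed".
- **TUGT.** "The walking aids were not allowed during the test". The result is again the average of three times. Arm use is not barred here: "MHD patients were seated in a back chair with armrests".

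Section 2.2 has patients "randomized into an intervention group of 25 cases and a control group of 25 cases" and fixes the visits: "Measure the indicators of each group at baseline, months 6, 12". Section 2.3 requires "Having free movement ability, and being able to tolerate Baduanjin exercise after cardiopulmonary exercise test", so patients should be testable at entry. Section 2.5 provides a t-test, or a nonparametric test if the data are not normal, at the 0.05 level. It defines no analysis set and no handling of unobtainable values. Section 3 lists reasons for leaving the trial but does not say how those patients are analysed, and it does not remove a patient who merely becomes weaker.

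**The concern.** A completion time exists only if the test is completed. A patient who can no longer rise five times with crossed arms, or walk the TUGT course without an aid, has no time, and neither test provides a cap, failure code or rank for that result. Choosing the nonparametric test of section 2.5 does not help by itself, because a rank test on available times omits the same patient.

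The other fitness tests have a natural poor end: grip strength can be low, forward flexion can be negative, and one-leg standing time can be close to zero. FTSST and TUGT do not.

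The missing results would be among the worst. If Baduanjin works, more controls than intervention patients would be unable. Removing them would improve the control mean and shrink the observed benefit. If inability were commoner in the intervention arm, the same omission would enlarge the apparent benefit.

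**Working it through.** **Inputs from the plan.** 25 patients per arm (section 2.2) and significance at P < 0.05 (section 2.5), taken as two-sided because sidedness is not stated. The plan gives no effect size, SD, power or inability rate, so there is no stated figure to reproduce.

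**Assumptions.** Times are normal in SD units, with higher meaning worse, and the slowest patients are the ones unable. The shares unable and the true benefits are assumed and shown as a range. One patient is 1/25 = 4% of an arm.

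**Step 1: bias for given shares unable.** Dropping the slowest share q lowers an arm's mean by φ(z)/(1 − q), where z is the upper-q normal quantile.

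- q = 4%: 0.090 SD
- q = 8%: 0.162 SD
- q = 12%: 0.227 SD
- q = 20%: 0.350 SD

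The bias in the control-minus-intervention difference is the intervention shift minus the control shift.

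- 8% vs 8%: 0
- 8% vs 4%: 0.090 − 0.162 = −0.072 SD
- 12% vs 4%: 0.090 − 0.227 = −0.14 SD
- 20% vs 4%: 0.090 − 0.350 = −0.26 SD
- 4% vs 12%: +0.14 SD (benefit overstated)

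For scale, the difference detectable with 80% power at 25 per arm is (1.96 + 0.84) × √(2/25) = 0.79 SD.

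**Step 2: shares that are consistent with the effect.** If one ability threshold applies to both arms, the control share and the true benefit together fix the intervention share. With 20% of controls unable, the threshold is 0.84 SD above the control mean. A benefit of 0.5 SD puts it 0.84 + 0.5 = 1.34 SD above the intervention mean, which leaves about 9% unable. A split of 20% vs 4% would need a benefit of about 1.75 − 0.84 = 0.91 SD.

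**Step 3: simulation with a common threshold.** 4,000 runs per row, 25 per arm. The rank test is Mann-Whitney, with all unable patients tied at the worst rank.

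| True benefit | Controls unable | Mean number unable (control / intervention) | Difference in available times | Power, t-test on available times | Power, unable ranked worst |
|---|---|---|---|---|---|
| 0.5 SD | 4% | 1.0 / 0.3 | 0.43 SD | 34.8% | 37.4% |
| 0.5 SD | 8% | 2.0 / 0.7 | 0.40 SD | 33.1% | 37.6% |
| 0.5 SD | 12% | 3.0 / 1.2 | 0.37 SD | 29.6% | 37.8% |
| 0.5 SD | 20% | 4.9 / 2.3 | 0.33 SD | 24.3% | 38.3% |
| 0.8 SD | 12% | 3.0 / 0.6 | 0.63 SD | 65.3% | 76.6% |
| 0.8 SD | 20% | 5.0 / 1.2 | 0.56 SD | 56.9% | 76.9% |

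The simulation error of a power near 25% is √(0.25 × 0.75/4,000), about 0.7 percentage points. If every patient had a time, t-test power would be about 39% to 41% at 0.5 SD and about 80% at 0.8 SD. With no true effect and equal shares unable, the mean difference is about zero and the type I error about 5% under either approach.

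**The case against.** The strongest reply is that the plan anticipates slowing and the tests measure slowing. Section 1 says "MHD patients gradually experience muscle atrophy, decreased upper limb motor ability, slow walking, and slow sitting and standing". A slower patient gets a longer time and stays in the analysis. This stands: a reader might infer that the described decline itself removes patients, but the documents mention neither loss of the ability to rise without arms nor dependence on aids. The gap concerns a further step, which is plausible over 12 months in patients aged up to 75 but is not quantified.

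Three further limits also stand.

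- No passage says that unable patients are dropped. That is inferred from silence: averaging three times and comparing the groups has this result unless a rule is added.
- The arm-support restriction belongs to FTSST alone. For TUGT, needing an aid in daily life is not the same as being unable to walk 3 m out and back without one.
- The entry criteria select mobile, stable patients, and some abrupt causes of inability are exit reasons under section 3. Few patients may be affected.

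It can also be said that this is one case of a wider silence on missing data. That is true, but a general missing-data rule would not settle it. An attending patient who cannot do the test has an observed bad outcome, not an unknown one.

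**Conclusion.** The point holds as a conditional risk to two of the five fitness tests. The plan has no value for an attending patient who cannot perform FTSST or TUGT as specified, and comparing available times would leave out some of the worst performers. The bias requires unequal inability between arms. A real benefit would produce that, and the bias would then run toward no effect.

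Under the assumptions above, the bias is about 0.14 SD at 12% vs 4% unable and about zero at equal shares. With a true benefit of 0.5 SD and 12% to 20% of controls unable, the observed difference is about 0.37 to 0.33 SD. Power falls to about 30% to 24%, against about 38% with worst ranking. If only about one control is unable, the loss is small (34.8% against 37.4%).

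Two stronger readings are not supported. A reader might conclude that these two measures no longer answer the main objective; without an inability rate, the documents support only that they may be biased. A reader might also pair a 0.5 SD benefit with 20% vs 4% unable, but under a common ability threshold that combination is not coherent (step 2).

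**What to change.** Add these rules to sections 2.4 and 2.5 before outcomes are seen:

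- At each visit, record *attended but unable to complete under the stated conditions*, with the reason, separately from missed visits, death, transplant and other missing data.
- Make the rank-based form of the nonparametric test in section 2.5 the planned between-group comparison for FTSST and TUGT from the outset, rather than choosing it only once someone turns out to be unable.
- Rank every unable patient worse than all completed times at that visit.
- Count a patient as unable if any of the three required trials is attempted and cannot be completed for physical reasons. Averaging only the completed trials would let a patient who fails two of them keep the better time, and so bring back the favourable bias.
- Report the number unable by arm and visit, with mean times among completers as description.

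The cost is a few sentences and one field on the case form, with no extra patients or visits. The test procedures do not change. The comparison becomes one of ranks instead of a mean difference in seconds. At a 0.5 SD benefit its simulated power is about 2 to 3 percentage points below a t-test in which every patient had a time (39.4% against 37.4% at 4% of controls unable, 41.3% against 38.3% at 20%).

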4.1 Ethical Approval

This clinical research protocol complies with the relevant provisions of the Helsinki Declaration regarding the protection of subject rights. This protocol, written informed consent form, and materials directly related to the subjects must be submitted to the ethics committee for written approval before the study can be officially conducted. If this protocol has been revised during the clinical research implementation process, it must be submitted to the ethics committee for approval before implementation, and these changes cannot be implemented without the approval of the ethics committee, unless they are made to eliminate obvious and direct risks to the subjects. When such situations occur, they will be reported to the ethics committee. If important new information related to the study is found, the informed consent form must be modified in writing and submitted to the ethics committee for approval before obtaining the consent of the subjects again. Each clinical research center agrees that before the start of this research project, the ethics committee of the team leader unit shall review the research plan. The ethics committees of each sub center may choose to file or review it themselves. If necessary (such as serious adverse events or protocol violations), the ethics committees of each center shall convene a meeting in a timely manner for review and report the review conclusions to the ethics committees of other

centers.

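### Does the garbled end-of-timing sentence leave the eyes-closed one-leg stand (SOLECT), one of six primary measures, without a usable stop rule?

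*Combined protocol and SAP*

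**What the plan says.** Section 2.4, under the heading "Primary Outcome Measure", numbers six items: grip strength, the five-times sit-to-stand test, the timed up-and-go, sitting forward flexion, SOLECT and bone mineral density. For SOLECT it describes the posture: arms spread, eyes closed, one leg supporting, the other bent. It then gives the timing as "from the time when the foot left the ground, and the shaking stopped when the foot left the ground or stood up". The summary rule is clear: "The average of the three times was used for statistical analysis".

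Section 2.2 names the test without a timing rule. It sets the schedule ("Measure the indicators of each group at baseline, months 6, 12") and the size ("A total of 50 MHD patients will be included and randomized"), with 25 patients per arm. No other section returns to how SOLECT is timed, and the leg to be tested is not stated.

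**The concern.** A timed test needs a start event and a stop event. Here the only candidate for the stop has shaking as its subject, so it never quite says that the clock stops. It repeats the start event, does not say whether the supporting or the raised foot is meant, and ends by mentioning standing up although the patient is already on one leg.

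The protocol looks more careful elsewhere. For the sit-to-stand test it says "They completed five sitting and standing movements, and the completion time was recorded", and the timed up-and-go finishes when the patient is seated again. The bone scan even fixes a side ("the left femur Ward triangle area"), while SOLECT fixes no leg.

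If assessors had to devise their own rule, times might not be comparable between assessors or across baseline, month 6 and month 12. SOLECT is the only primary item described as measuring static posture, so no other primary measure would replace it. Extra noise would be unwelcome with 25 patients per arm. If the rule in use differed between arms, the comparison would be biased.

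**Working it through.** The plan gives no figure to reproduce, so the check is mainly one of reading, followed by a count and a short argument about where an ambiguous stop rule could act.

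**1. The literal reading.** Start: a foot leaves the floor. Stop: a foot leaves the floor. If both are the same foot at the same moment, every recorded time is zero. No assessor could apply that and record a usable result, so the literal reading cannot be what is done. The question is whether a sensible reading exists.

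**2. The sensible readings.**
- *Which foot.* To begin a one-leg stand, the raised foot must leave the floor, so the start event concerns the raised foot. The raised foot is then already off the floor, so a second event of a foot leaving the floor can only concern the supporting foot, which shifts or hops.
- *Standing up.* From a one-leg position with the other leg bent, this can mean coming back to stand on both feet, that is, the raised foot coming down. That ends a one-leg stand.
- *How the two relate.* The sentence joins them with *or*. They need not be rival interpretations: they can be alternative ends, with the clock stopping at whichever comes first.

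This uses only the words on the page and the posture described just before them. The word *shaking* remains unexplained, but the rule does not need it.

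**3. The comparisons with other items.**
- *Sit-to-stand.* The text asks for five completed movements but does not say whether the clock stops at the fifth stand or the fifth sit. It too leaves a detail to the assessor, so it is a weak benchmark.
- *Femur scan.* A side named for an imaging region says nothing about how a balance test is given. Grip strength is measured in both hands. Not naming a leg for SOLECT omits a detail but contradicts nothing.

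**4. The count.** Inputs from Sections 2.2 and 2.4: 50 patients, 3 visits, 3 attempts averaged.
- Averaged values: 50 × 3 = 150.
- Timed attempts: 150 × 3 = 450, or 25 × 3 × 3 = 225 per arm, before drop-out.
- This assumes one leg per patient. Testing both legs would give 2 × 450 = 900.

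These figures show how much data use the definition. They do not measure any error in it.

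**5. What an ambiguous rule could do to the comparison.** Section 2.5 compares the two groups by a t-test or a nonparametric test.
- If the rule used at a visit lengthens every time by the same amount *d* in both arms, the difference in means is (A + *d*) − (B + *d*) = A − B. A rank comparison is also unchanged. This includes a rule that shifts between visits but is shared by the arms.
- If the rule varies haphazardly between patients and adds variance *s*² to each patient's value (independence assumed), the variance of the difference in means rises by *s*²/25 + *s*²/25 = 0.08 *s*². The documents give no SD or reliability for SOLECT, so *s* is unknown and the loss cannot be put in seconds or in power.
- Bias needs a rule that differs by arm. The documents show no such difference.

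**The case for a change.** The strongest reply is that this sentence is the operational definition of a listed primary measure, so a probable translation cause does not make it cosmetic. A reader of the public document cannot confirm which end point was used. The candidate events can occur at different moments in the same attempt. No section describes blinding of outcome assessors, so a difference between arms cannot be ruled out. A correction would cost one sentence, one line on the case observation form and ethics committee approval if the study is under way.

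Much of this stands. The sentence is garbled, nothing else in the documents repairs it, and a reader would be better served by clear English. The step from there to a defect in the trial does not stand. It needs assessors to work from this English text alone and to choose different rules. The trial is run at a hospital in China, and a Chinese-language template placeholder left in Section 2.6 suggests that the English derives from a Chinese document. A clear rule may exist there or in site practice. The number of assessors is not stated either, so variation between them is also an assumption. The missing statement on blinding is a separate matter, because a clearer stop sentence would not blind anyone.

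Writing in new stop events is also not free of risk. Under Section 4.1 a revision made during the study is not immediate: "it must be submitted to the ethics committee for approval before implementation". If one rule is already in use, a different one brought in partway would create the inconsistency across visits that the concern seeks to prevent.

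**Conclusion.** This is a clerical fault in the English text, probably from translation, and a gap that trained assessors fill sensibly. The end-of-timing clause is ambiguous but not unusable: movement of the supporting foot or return to two-leg standing is a natural reading and a workable rule. The fault touches one of six primary items. No sample size, error rate, analysis method or conclusion is shown to be wrong or weaker because of it, and any loss of precision cannot be calculated from the documents.

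The conclusion rests on two assumptions that the documents neither confirm nor contradict: that assessors work from a source-language text or site practice with an ordinary stop rule, and that the rule is the same in both arms. Evidence that the rule differed by arm would reopen the point. Without it, no change to the plan is called for. Rendering the sentence more faithfully from the source language would be editorial tidying.
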